10.8. Analysis of safety

Analysis of safety relative to the primary epoch will include analysis of safety data collected following administration of the three primary doses of study vaccine. Analysis of safety relative to the booster epoch will include analysis of safety data collected following administration of the booster dose of study vaccine. At this second stage, in

order to avoid missing SAEs that have been reported, an SAE summary table including all the events reported during the entire study period will also be generated.

The analysis will be based on the Total vaccinated cohort for both primary and booster epochs. All analyses are descriptive.

- The overall percentage of subjects/doses with at least one local symptom (solicited or unsolicited), with at least one general symptom (solicited or unsolicited) and with any symptom (solicited or unsolicited) during the 4-day (Days 0-3) solicited follow-up period will be tabulated with exact 95% CI [Clopper, 1934] after each vaccine dose and overall primary doses. The same calculations will be done for symptoms (solicited or unsolicited) rated as grade 3 in intensity, for symptoms (solicited or unsolicited) leading to medical advice and for symptoms (solicited or unsolicited) assessed as causally related to vaccination.
- The overall percentage of subjects/doses and of subjects reporting each individual solicited local and general symptom during the 4-day (Days 0-3) solicited follow-up period will be tabulated after each vaccine dose and overall primary doses, with exact 95% CI [Clopper, 1934] after each vaccine dose and overall primary doses. The same calculations will be done for each individual solicited symptom rated as grade 3 in intensity and for each individual solicited symptom assessed as causally related to vaccination.
- Occurrence of fever will be reported per 0.5°C cumulative increments.

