2. STUDY DESIGN

Study Group:	DTPa-IPV/Hib Group (N=235)				
Study Vaccine:	Infanrix-IPV/Hib				
Visit:	Visit 1	Visit 2	Visit 3	Visit 4	Visit 5
Time-points:	Day 0	Month 1.5	Month 3	Month 4	Month 15
Age of subjects:	3 months	4.5 months	6 months	7 months	18 months
Vaccination and BS:	V1	V2	V3	Post-Pri BS	Booster
Epochs:	← Primary epoch →			← Booster epoch →	

V = Primary vaccination

BS = Blood Sample

Post-Pri = One month after the third dose of primary vaccination course

Post-Booster = One month after booster vaccination

Protocol waivers or exemptions are not allowed with the exception of immediate safety concerns. Therefore, adherence to the study design requirements, including those specified in the outline of study procedures (Section 5.5 from the protocol), are essential and required for study conduct.

- Experimental design: Phase III, open-label, multi-centric, single-country study with a single group.
- Duration of the study: The intended duration of the study is approximately 16 months, per subject.
 - Epoch 001 (Primary epoch): Primary phase starting at Visit 1 (Day 0) and ending at Visit 4 (Month 4).
 - Epoch 002 (Booster epoch): Booster phase starting at Visit 5 (Month 15) and ending at Visit 6 (Month 16).

Study group: The study group and epochs foreseen in the study are presented in [Table 1](#).

Table 1 Study group and epochs foreseen in the study

Study group	Number of subjects	Age (Min/Max)	Epochs	
			Epoch 001 (Primary epoch)	Epoch 002 (Booster epoch)
DTPa-IPV/Hib Group	~ 235	3 months - 4 months	x	
DTPa-IPV/Hib Group	~ 235	18 months – 19 months		x

The study group and treatment foreseen in the study are presented in [Table 2](#).

Table 2 Study group and treatment foreseen in the study

Treatment name	Vaccine/Product name	Study Group
		DTPa-IPV/Hib Group
Infanrix-IPV/Hib	DTPa-IPV	x
	Hib	x

- Control: uncontrolled.
- Treatment group and vaccination schedule: All subjects will receive three doses of primary vaccination at 3, 4.5 and 6 months of age and a single dose of booster vaccination at 18 months of age.
 - DTPa-IPV/Hib Group: Subjects who will receive DTPa-IPV/Hib vaccine (*Infanrix-IPV/Hib*).
- Blinding: This is an open-label study (Refer to [Table 3](#)).

Table 3 Blinding of study epochs

Study Epochs	Blinding
Epoch 001 (Primary epoch)	open
Epoch 002 (Booster epoch)	open

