6.4. Analysis of safety**6.4.1. Analysis of safety planned in the protocol**

Analysis of safety relative to the primary epoch will include analysis of safety data collected following administration of the three primary doses of study vaccine. Analysis of safety relative to the booster epoch will include analysis of safety data collected following administration of the booster dose of study vaccine. At this second stage, in order to avoid missing SAEs that have been reported, an SAE summary table including all the events reported during the entire study period will also be generated.

The analysis will be based on the Total vaccinated cohort for both primary and booster epochs. All analyses are descriptive.

- The overall percentage of subjects/doses with at least one local symptom (solicited or unsolicited), with at least one general symptom (solicited or unsolicited) and with any symptom (solicited or unsolicited) during the 4-day (Days 0-3) solicited follow-up period will be tabulated with exact 95% CI after each vaccine dose and overall primary doses. The same calculations will be done for symptoms (solicited or unsolicited) rated as grade 3 in intensity, for symptoms (solicited or unsolicited) leading to medical advice and for symptoms (solicited or unsolicited) assessed as causally related to vaccination.
- The overall percentage of subjects/doses and of subjects reporting each individual solicited local and general symptom during the 4-day (Days 0-3) solicited follow-up period will be tabulated after each vaccine dose and overall primary doses, with exact 95% CI after each vaccine dose and overall primary doses. The same calculations will be done for each individual solicited symptom rated as grade 3 in intensity and for each individual solicited symptom assessed as causally related to vaccination.
- Occurrence of fever will be reported per 0.5°C cumulative increments.

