- The verbatim reports of unsolicited AEs will be reviewed by a physician and the signs and symptoms will be coded according to MedDRA. Every verbatim term will be matched with the appropriate Preferred Term. The percentage of subjects with unsolicited AEs occurring within 31-day (Days 0-30) follow-up period after any dose (after primary or booster vaccination) with its exact 95% CI will be tabulated by preferred term. Similar tabulation will be done for unsolicited AEs rated as grade 3, for unsolicited AEs with causal relationship to vaccination and AE(s)/SAE(s) leading to withdrawal from the study.
- The percentage of subjects who receive at least one concomitant medication during the 4-day (Days 0-3) solicited follow-up period and during the entire primary/booster epoch will be tabulated (with exact 95% CI after each vaccine dose and overall).
- Any large injection site reaction (defined as a swelling with a diameter > 50 mm, noticeable diffuse swelling or noticeable increase in limb circumference) after booster vaccination will be described in detail.

SAE(s) will be described in detail.

Handling of missing data:

- For a given subject and the analysis of solicited symptoms four days post-vaccination, missing or non-evaluable measurements will not be replaced. Therefore the analysis of the solicited symptoms based on the TVC will include only vaccinated subjects and doses with documented safety data (i.e., symptom screen completed).
- For analysis of unsolicited AEs, such as SAEs or AEs by primary Medical Dictionary for Regulatory Activities (MedDRA) term, and for the analysis of concomitant medications, all vaccinated subjects will be considered. Subjects, who do not report the event or the concomitant medication, will be considered as subjects without the event or the concomitant medication, respectively.
- For summaries reporting both solicited symptoms and unsolicited AEs, all vaccinated subjects will be considered. Subjects, who do not report the event or the concomitant medication, will be considered as subjects without the event or the concomitant medication, respectively.

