	3	Severe: Not eating at all

*Fever is defined as temperature $\geq 37.5^{\circ}\text{C} / 99.5^{\circ}\text{F}$ for oral, axillary or tympanic route, or $\geq 38.0^{\circ}\text{C} / 100.4^{\circ}\text{F}$ for rectal route.

The maximum intensity of local injection site redness/swelling will be scored at GSK Biologicals as follows:

0	:	Absent
1	:	≤ 5 mm
2	:	> 5 mm and ≤ 20 mm
3	:	> 20 mm

CONFIDENTIAL

116194 [DTPA-IPV (INFANRIX-IPV)-061]

Statistical Analysis Plan Amendment 2 Final

The maximum intensity of fever will be scored at GSK Biologicals as follows:

Axillary/Tympanic/Oral

0	:	< 37.5°C / 99.5°F
1	:	≥ 37.5°C / 99.5°F and ≤ 38.0°C / 100.4°F
2	:	> 38.0°C / 100.4°F and ≤ 39.0°C / 102.2°F
3	:	> 39.0°C / 102.2°F

In case temperature is recorded rectally, a conversion to Axillary temperature will be performed by removing 0.5°C.

Note that for all tables described in this section, the way the percentage of subjects will be derived will depend on the event analysed (see table below for details). As a result, the N value will differ from one table to another.

Event	N used for deriving % per subject for Vaccination phase	N used for deriving % per dose for Vaccination phase
Concomitant vaccination	All subjects with study vaccine administered	All study visits with study vaccine administered
Solicited general symptom	All subjects with solicited symptoms documented as present or absent for at least one dose.	All doses with solicited symptoms documented as present or absent within 0-3 days post dose
Unsolicited symptom	All subjects with study vaccine administered	All study visits with study vaccine administered
Concomitant medication	All subjects with study vaccine administered	All study visits with study vaccine administered

For summaries by MedDRA primary preferred term combining solicited and unsolicited adverse events, solicited adverse events will be coded as per the following MedDRA codes

Solicited symptom	Lower level term code	Corresponding Lower level term decode
Drowsiness	10013649	Drowsiness
Fever	10016558	Fever
Irritability/Fussiness	10022998	Irritability
Loss of appetite	10003028	Appetite lost
Pain	10022086	Injection site pain
Redness	10022098	Redness at injection site
Swelling	10053425	Swelling at injection site

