Pain	All	224	81	36.2	29.9	42.8	227	88	38.8	32.4	45.4
	Grade 3	224	3	1.3	0.3	3.9	227	3	1.3	0.3	3.8
Redness (mm)	All	224	131	58.5	51.7	65.0	227	124	54.6	47.9	61.2
	>20	224	20	8.9	5.5	13.5	227	18	7.9	4.8	12.2
Swelling (mm)	All	224	85	37.9	31.6	44.7	227	78	34.4	28.2	40.9
	>20	224	9	4.0	1.9	7.5	227	4	1.8	0.5	4.5
Dose 6											
Pain	All	224	87	38.8	32.4	45.6	227	78	34.4	28.2	40.9
	Grade 3	224	1	0.4	0.0	2.5	227	3	1.3	0.3	3.8
Redness (mm)	All	224	128	57.1	50.4	63.7	227	122	53.7	47.0	60.4
	>20	224	14	6.3	3.5	10.3	227	14	6.2	3.4	10.1
Swelling (mm)	All	224	96	42.9	36.3	49.6	227	88	38.8	32.4	45.4
	>20	224	6	2.7	1.0	5.7	227	7	3.1	1.2	6.3
Overall/dose											
Pain	All	672	276	41.1	37.3	44.9	681	279	41.0	37.2	44.8
	Grade 3	672	9	1.3	0.6	2.5	681	14	2.1	1.1	3.4
Redness (mm)	All	672	392	58.3	5	62.1	681	365	53.6	49.8	57.4
	>20	672	38	5.7	4.0	7.7	681	35	5.1	3.6	7.1
Swelling (mm)	All	672	246	36.6	33.0	40.4	681	230	33.8	30.2	37.5
	>20	672	20	3.0	1.8	4.6	681	13	1.9	1.0	3.2
Overall/subject											
Pain	All	224	143	63.8	57.2	70.1	227	146	64.3	57.7	70.5
	Grade 3	224	9	4.0	1.9	7.5	227	12	5.3	2.8	9.1
Redness (mm)	All	224	177	79.0	73.1	84.2	227	167	73.6	67.3	79.2
	>20	224	29	12.9	8.8	18.1	227	26	11.5	7.6	16.3
Swelling (mm)	All	224	130	58.0	51.3	64.6	227	121	53.3	46.6	59.9
	>20	224	15	6.7	3.8	10.8	227	11	4.8	2.4	8.5

Combo group = Subjects received DTPa-IPV/Hib vaccine as a single injection at 2, 4 and 6 months of age

Control group = Subjects received DTPa-IPV and Hib vaccines at different injection sites at 2, 4 and 6 months of age

For each dose and overall/subject:

N = number of subjects with at least one documented dose

n% = number/percentage of subjects reporting the symptom at least once

For Overall/dose:

N = number of documented doses

n% = number/percentage of doses followed by at least one type of symptom

95%CI = Exact 95% confidence interval; LL = lower limit, UL = upper limit

Dose 2, 4 and 6 are the doses where subjects has received study vaccine - DTPa-IPV/Hib vaccine in Combo group and DTPa-IPV and Hib in Control group

Grade 3 pain refers to severe significant pain at rest. Prevents normal every day activities.

CONFIDENTIAL
 116194 [DTPA-IPV (INFANRIX-IPV)-061]
 Statistical Analysis Plan Amendment 2 Final

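### In the per-subject rate over the primary course, an unreturned diary card for an administered dose counts as no symptom, which can only lower the rate among the infants included

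*SAP*

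**What the plan says.** The primary course is three doses: "All subjects will receive three doses of primary vaccination at 3, 4.5 and 6 months of age" (SAP Section 2). Protocol Section 10.8 plans each individual solicited symptom so that it "will be tabulated after each vaccine dose and overall primary doses", and SAP Section 6.4.1 repeats this with exact confidence intervals: "will be tabulated after each vaccine dose and overall primary doses, with exact 95% CI after each vaccine dose and overall primary doses". Grade 3 and related symptoms are treated in the same way.

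The denominators for solicited general symptoms are in the table in SAP Section 11.2.5:

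- Per subject: "All subjects with solicited symptoms documented as present or absent for at least one dose".
- Per dose: "All doses with solicited symptoms documented as present or absent within 0-3 days post dose".

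That table has no row for local symptoms. The nearest statement is the footnote to Template 13 in Annex 3, which for each dose and for the overall/subject rows gives "N = number of subjects with at least one documented dose" and "n% = number/percentage of subjects reporting the symptom at least once". Annex 3 says that its templates come from other studies and are illustrative.

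On missing data for solicited symptoms, SAP Section 6.4.1 says "missing or non-evaluable measurements will not be replaced" and limits the analysis to subjects and doses with documented data. The opening paragraph of Section 11.2.5 says something different: it puts all vaccinated subjects into the solicited analysis and treats a subject with no report as having no event.

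**The concern.** The overall per-subject rate answers the question of what share of infants had the symptom after at least one primary dose. To answer no for an infant, every dose that the infant received has to have been observed. The planned denominator asks for only one observed dose. If the one returned card is symptom-free and the others are missing, the infant is scored as reaction-free over the course.

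The per-dose denominator avoids this, because an undocumented dose leaves both numerator and denominator. In the per-subject rate it leaves only the chance of an event.

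The trial is uncontrolled, so there is no second arm in which the same shortfall could cancel. These rates will be read as absolute figures.

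**Working it through.** **Plan's own figures.** The documents state no expected symptom rate and no card-return rate, so there is no planned value to reproduce here. The only planning allowance is 200/0.85 = 235.3, which agrees with the stated 235. It concerns evaluability for immunogenicity, not diary cards, and is not used below.

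**Inputs.** Three primary doses (SAP Section 2) and the denominator and numerator rules above. The following are assumptions: a per-dose symptom probability p of 20% or 40%; correlation ρ between an infant's doses of 0 or 0.4; and a share s of infants with one documented dose and the same share s with two, the rest having three. All infants are taken to have received three doses, and card return is taken as unrelated to symptoms.

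The upper ρ is only loosely anchored. Template 13's borrowed figures for pain are 276/672 = 41.1% per dose and 143/224 = 63.8% per subject, against 1 − (1 − 0.411)³ = 79.5% under independence. That implies ρ of about 0.39. It is not evidence for this trial.

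**Formulas.** Let A(k) be the probability of at least one event in k doses.

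- Independent doses: A(k) = 1 − (1 − p)^k.
- Correlated doses (beta-binomial): a = p(1/ρ − 1), b = (1 − p)(1/ρ − 1), and A(k) = 1 − the product over j = 0 to k − 1 of (b + j)/(a + b + j).
- Rate under the planned denominator: R = s·A(1) + s·A(2) + (1 − 2s)·A(3), to be compared with A(3).

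**Worked case, p = 40%, s = 5%.**

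- Independent: A = 40.0%, 64.0%, 78.4%. R = 0.05×40.0 + 0.05×64.0 + 0.90×78.4 = 75.8%, a loss of 2.6 points.
- ρ = 0.4: a = 0.6, b = 0.9. The probability of no event in 1, 2 and 3 doses is 0.600, 0.456 and 0.378, so A = 40.0%, 54.4%, 62.2%. R = 60.7%, a loss of 1.5 points.

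| p per dose | ρ | Full-course rate | Reported, s = 1% | Reported, s = 5% | Loss at s = 5% (points) |
|---|---|---|---|---|---|
| 40% | 0 | 78.4% | 77.9% | 75.8% | 2.6 |
| 40% | 0.4 | 62.2% | 61.9% | 60.7% | 1.5 |
| 20% | 0 | 48.8% | 48.4% | 46.7% | 2.1 |
| 20% | 0.4 | 35.6% | 35.4% | 34.6% | 1.1 |

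At s = 1% the loss is 0.2 to 0.5 point. At p = 2%, as for a rare grade 3 symptom, the loss at s = 5% is 0.1 to 0.3 point.

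**The single infant.** Given one symptom-free card and two unseen administered doses, the chance of at least one unseen reaction is 1 − [1 − A(3)]/[1 − A(1)]. At p = 40% this is 1 − 0.216/0.6 = 64% for independent doses, or 1 − 0.378/0.6 = 37% at ρ = 0.4. The planned rule scores it as zero.

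**The conflicting rules give different answers.** Take hypothetical counts of 235 infants, all given three doses: 200 with full cards (120 with a reaction), 23 with one symptom-free card and two missing, and 12 with no card.

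- Section 11.2.5 table: 120/223 = 53.8%.
- Section 11.2.5 opening paragraph: 120/235 = 51.1%.
- Infants with every card returned: 120/200 = 60.0%.

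**The case against.** The strongest case is that the effect is small, largely disclosed and decides nothing. The denominator is stated openly. Cards are collected and checked at Visits 2, 3 and 4, and unreturned cards are chased (Protocol Section 5.6.15). Per-dose rates are sound. Doses administered are to be tabulated, and a mock table covers card compliance. All analyses are descriptive. Even a loss of 1 to 2.6 points is small beside the sampling error: the exact 95% interval for 141/235 = 60% runs from 53.4% to 66.3%. All of this stands and keeps the point minor. It does not remove the point, because compliance is shown per dose and so does not tell a reader how many infants have one, two or three documented doses.

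It can also be argued that nothing is formally replaced, since the Template 13 numerator counts only symptoms reported. That is fair as a label for a reported rate. As a rate over the course, the result is the same as scoring the missing card as absent.

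Three stronger readings are tempting, and the documents do not support them:

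- **The rate is biased down against all vaccinated infants.** The direction is certain only among included infants. Infants with no card leave the denominator, and if return depends on symptoms that selection can act either way.
- **Doses not given are also scored as symptom-free.** A dose not given has no reaction to miss. The safety cohort is defined by at least one primary dose, so this is incomplete exposure, and pooling it with unreturned cards overstates the problem.
- **Course rates should be quoted from infants with all three doses documented.** Protocol Section 6.5 bars further doses after certain reactions, so that group loses reactors by design. Hypothetically, if 10 of 235 infants have grade 3 fever, 3 of those 10 stop vaccination and all cards are returned, the planned rate is 10/235 = 4.3%, while the all-three group gives 7/232 = 3.0%.

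**Conclusion.** The point holds in a limited form. For solicited general symptoms, the per-subject rate over the primary course treats an unreturned card for an administered dose as no symptom, which does not fit the missing-data rule in SAP Section 6.4.1. The extension to local symptoms rests on an illustrative template, not on a stated rule. Within included infants the effect is one-directional.

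The size cannot be fixed from the documents. It is negligible if nearly all cards come back and reaches a few points for common symptoms only if a material share of infants have incomplete cards. The illustrations assume that all infants received three doses and that card return is unrelated to symptoms. Separately, Section 11.2.5 contradicts itself on who is in the solicited analysis. That needs settling whatever the return rate.

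**What to change.** In SAP Section 11.2.5:

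1. Keep the planned overall/subject row.
2. Add a supplementary overall/subject row for each solicited symptom, with N = infants for whom every primary dose they received is documented. Infants who stopped after a reaction then stay in if their cards are complete.
3. Footnote the number of infants by primary doses received (1, 2, 3) and by doses documented (1, 2, 3), so that incomplete exposure and missing cards can be told apart.
4. Do not make a row restricted to three documented doses the quoted course rate.
5. Reconcile the opening paragraph with Section 6.4.1 and with the denominator table, and state the denominator for local symptoms in that table instead of leaving it to Template 13.

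The cost is one extra row per symptom and a footnote, with no new data and no change to sample size or conduct. The added row has its own limit: it is unbiased only if card return is unrelated to symptoms, and infants with fewer doses have fewer cards to lose, so they are slightly over-represented. Both rows should therefore be shown together. If they agree, the question is closed.

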12. ANNEX 2: SUMMARY ON ELIMINATION CODES

Refer to section 5.1.1

13. ANNEX 3: STUDY SPECIFIC MOCK TFL

The following draft study specific mock TFLs will be used.

The data display, title and footnote are for illustration purpose and will be adapted to the study specificity as indicated in the TFL TOC.

These templates were copied from recent studies. Note that there may be few changes between the study specific SAP mock TFL and the final TFLs. These editorial/minor changes will not lead to a SAP amendment.

CONFIDENTIAL

116194 [DTPA-IPV (INFANRIX-IPV)-061]
 Statistical Analysis Plan Amendment 2 Final

Template 1 Number of subjects enrolled by center – TVC

Center	Combo group		Control group		Total	
	n	n	n	n	%	
PPD	20	21		41	9.1	
PPD	27	28		55	12.2	
PPD	7	7		14	3.1	
PPD	16	16		32	7.1	
PPD	27	26		53	11.8	
PPD	26	26		52	11.5	
PPD	25	25		50	11.1	
PPD	23	24		47	10.4	
PPD	22	22		44	9.8	
PPD	24	25		49	10.9	
PPD	7	7		14	3.1	
All	224	227		451	100	

<group description>

n = number of subjects included in each group or in total for a given center or for all centers

All = sum of all subjects in each group or in total (sum of all groups)

% = n/All x 100

Template 2 Number of subjects vaccinated, completed and withdrawn with reason for withdrawal at Visit 3 - TVC

	HRV Liq	HRV LYO	Total
Number of subjects vaccinated	300	300	1200
Number of subjects completed	298	297	1193
Number of subjects withdrawn	2	3	7
Reasons for withdrawal :			
Serious Adverse Event	0	1	1
Non-serious adverse event	0	0	0
Protocol violation	0	0	0
Consent withdrawal (not due to an adverse event)	1	2	4
Migrated/moved from study area	1	0	2
Lost to follow-up (subjects with incomplete vaccination course)	0	0	0
Lost to follow-up (subjects with complete vaccination course)	0	0	0
Others	0	0	0

HRV LIQ = HRV vaccine liquid formulation

HRV LYO = HRV vaccine HRV Lyophilised formulation

Vaccinated = number of subjects who were vaccinated in the study

Completed = number of subjects who completed study visit 3

Withdrawn = number of subjects who did not come for study visit 3

CONFIDENTIAL
 116194 [DTPA-IPV (INFANRIX-IPV)-061]
 Statistical Analysis Plan Amendment 2 Final

Template 3 Number of subjects at each visit and list of withdrawn subjects (TVC)

Group	VISIT	N	Withdrawn Subject numbers	Reason for withdrawal
HRV Liq	VISIT 1	508		
			no. PP	CONSENT WITHDRAWAL
			no. PP	CONSENT WITHDRAWAL
			no. PPD	CONSENT WITHDRAWAL
	VISIT 2	504	no. PPD	CONSENT WITHDRAWAL
			no. PPD	CONSENT WITHDRAWAL
			no. PPD	CONSENT WITHDRAWAL
				SERIOUS ADVERSE EXPERIENCE
	VISIT 3	501		
			no. P	MIGRATION FROM STUDY AREA
			no. PP	CONSENT WITHDRAWAL
			no. PP	MIGRATION FROM STUDY AREA
			no. PP	CONSENT WITHDRAWAL
			no. PP	MIGRATION FROM STUDY AREA
			no. PPD	CONSENT WITHDRAWAL
			no. PPD	MIGRATION FROM STUDY AREA
			no. PPD	MIGRATION FROM STUDY AREA
HRV Lyo	VISIT 1	257		
			no. PP	PROTOCOL VIOLATION
			no. PPD	CONSENT WITHDRAWAL
	VISIT 2	255	no. PPD	CONSENT WITHDRAWAL
			no. PP	MIGRATION FROM STUDY AREA
			no. PP	LOST TO FOLLOW-UP
	VISIT 3	254	no. PP	LOST TO FOLLOW-UP
			no. PP	CONSENT WITHDRAWAL
			no. PP	MIGRATION FROM STUDY AREA
			no. PPD	LOST TO FOLLOW-UP
			no. PPD	ADVERSE EXPERIENCE
	VISIT 4	247		

CONFIDENTIAL
 116194 [DTPA-IPV (INFANRIX-IPV)-061]
 Statistical Analysis Plan Amendment 2 Final

Template 4 Number of subjects enrolled into the study as well as the number of subjects excluded from ATP analyses with reasons for exclusion

Title	Total				HRV LIQ			HRV LYO		
	N	n	s	%	N	n	s	N	n	s
Total enrolled cohort	1200				300			300		
TVC	1200			100	300			300		
Administration of vaccine(s) forbidden in the protocol (code 1040)		2	2			0	0		0	0
Study vaccine dose not administered according to protocol (code 1070)		73	73			23	23		16	16
Initially seropositive or unknown anti-rotavirus IgA antibody on day of dose 1 (code 1500)		10	11			3	3		1	1
Protocol violation (inclusion/exclusion criteria) (code 2010)		1	1			1	1		0	0
Administration of any medication forbidden by the protocol (code 2040)		1	1			0	0		1	1
Underlying medical condition forbidden by the protocol (code 2050)		1	1			0	0		0	0
Concomitant infection not related to the vaccine which may influence immune response (code 2070)		0	1			0	0		0	1
Non compliance with vaccination schedule (including wrong and unknown dates) (code 2080)		14	16			6	7		3	4
Non compliance with blood sampling schedule (including wrong and unknown dates) (code 2090)		12	16			3	5		4	5
Essential serological data missing (code 2100)		87	95			20	22		23	26
Subjects with incomplete study vaccination schedule but with post serological result (code 2500)		1	1			0	0		0	0
ATP	998			83.2	244			252		

HRV LIQ = HRV vaccine liquid formulation Lot C HRV LYO = HRV vaccine HRV Lyophilised formulation

Note: Subjects may have more than one elimination code assigned

n = number of subjects with the elimination code assigned excluding subjects who have been assigned a lower elimination code number

s = number of subjects with the elimination code assigned

% = percentage of subjects in the per protocol set (ATP) relative to the TVC (ES)

CONFIDENTIAL

116194 [DTPA-IPV (INFANRIX-IPV)-061]
 Statistical Analysis Plan Amendment 2 Final

Template 5 Deviations from specifications for age and intervals between study visits - TVC

		Age	PRE-Dose:1	Dose:1-Dose:2		Dose:2-PII(M2)	
Group	Protocol	Protocol	Protocol	Adapted	Protocol	Adapted	
HRV LIQ	from 10 to 17 weeks	from 0 to 0 days	from 30 to 48 days	from 21 to 48 days	from 30 to 48 days	from 21 to 48 days	
	N	300	300	300	291	291	
	n	1	1	8	7	4	
	%	0.3	0.3	2.7	2.3	1.4	
HRV LYO	range	9 to 17	0 to 9	27 to 76	27 to 76	30 to 56	30 to 56
	N	300	300	299	299	289	289
	n	0	2	4	4	5	3
	%	0.0	0.7	1.3	1.3	1.7	1.0
range		10 to 16	0 to 3	30 to 61	30 to 61	28 to 61	28 to 61

HRV LIQ = HRV vaccine liquid formulation Lot A

HRV LIQ = HRV vaccine liquid formulation Lot B

HRV LIQ = HRV vaccine liquid formulation Lot C

HRV LYO = HRV vaccine HRV Lyophilised formulation

PRE = pre-vaccination

PII (M2) = blood sample taken one month after Dose 2 of the HRV vaccine (Visit 3)

Adapted = interval used for defining the ATP cohorts for immunogenicity

N = total number of subjects with available results

n/% = number / percentage of subjects with results outside of the interval

range = minimum-maximum for age and intervals

Template 6 Summary of demographic characteristics (ATP cohort for Immunogenicity)

		HRV LIQ N = 244		HRV LYO N = 252		Total N = 998	
Characteristics	Parameters or Categories	Value or n	%	Value or n	%	Value or n	%
Age at Dose 1 of HRV vaccine (weeks)	Mean	11.5	-	11.6	-	11.6	-
	SD	1.19	-	1.20	-	1.22	-
	Median	11.0	-	11.0	-	11.0	-
	Minimum	10	-	10	-	10	-
	Maximum	15	-	16	-	17	-
Age at Dose 2 of HRV vaccine (weeks)	Mean	16.5	-	16.7	-	16.6	-
	SD	1.37	-	1.34	-	1.40	-
	Median	16.0	-	17.0	-	17.0	-
	Minimum	14	-	14	-	14	-
	Maximum	20	-	21	-	22	-
Gender	Female	120	49.2	120	47.6	483	48.4
	Male	124	50.8	132	52.4	515	51.6
Ethnicity	American Hispanic or Latino	1	0.4	0	0.0	3	0.3
	Not American Hispanic or Latino	243	99.6	252	100.0	995	99.7
Race	African heritage / African American	1	0.4	0	0.0	2	0.2
	American Indian or Alaskan native	0	0.0	0	0.0	0	0.0
	Asian - central/south Asian heritage	0	0.0	0	0.0	0	0.0
	Asian - east Asian heritage	0	0.0	0	0.0	0	0.0
	Asian - Japanese heritage	0	0.0	0	0.0	0	0.0
	Asian - south east Asian heritage	0	0.0	0	0.0	0	0.0
	Native Hawaiian or other pacific islander	0	0.0	0	0.0	0	0.0
	White - Arabic / north African heritage	2	0.8	0	0.0	2	0.2
	White - Caucasian / European heritage	240	98.4	247	98.0	984	98.6
	Other	1	0.4	5	2.0	10	1.0
Height at Visit 1 (cm)	Mean	60.7	-	60.6	-	60.5	-
	SD	2.32	-	2.22	-	2.32	-
	Median	61.0	-	61.0	-	61.0	-
	Unknown	2	-	0	-	3	-
Weight at Visit 1 (kg)	Mean	6.2	-	6.1	-	6.1	-
	SD	0.77	-	0.75	-	0.76	-
	Median	6.2	-	6.1	-	6.1	-
BMI at Visit 1 (kg/m²)	Mean	16.7	-	16.7	-	16.6	-
	SD	1.46	-	1.46	-	1.47	-
	Median	16.5	-	16.7	-	16.5	-
	Unknown	2	-	0	-	3	-

HRV LIQ = HRV vaccine liquid formulation Lot A

HRV LIQ = HRV vaccine liquid formulation Lot B

HRV LIQ = HRV vaccine liquid formulation Lot C

HRV LYO = HRV vaccine HRV Lyophilised formulation

N = total number of subjects

n (%) = number / percentage of subjects in a given category

Value = value of the considered parameter

SD = standard deviation

Template 7 Study population (TVC)

Study population (Total vaccinated cohort)		
Number of subjects	Combo group	Control group
Planned, N	225	225
Randomised, N (Total Vaccinated Cohort)	224	227
Completed, n (%)	224 (100)	227 (100)
Demographics	Combo group	Control group
N (Total Vaccinated Cohort)	224	227
Females :Males	97:127	115:112
Mean Age, weeks (SD)	8.8 (1.1)	8.8 (1.1)
Median Age, weeks (minimum, maximum)	9 (7, 11)	9 (7, 11)
Most frequent race: Asian - East Asian Heritage, n (%)	224 (100)	226 (99.6)

Combo group = Subjects received DTPa-IPV/Hib vaccine as a single injection at 2, 4 and 6 months of age

Control group = Subjects received DTPa-IPV and Hib vaccines at different injection sites at 2, 4 and 6 months of age

N = Total number of subjects enrolled in the study

n/% = Number/percentage of subjects in a given category

SD = Standard Deviation

MeaAge = Age calculated from Date of birth to first study vaccination

Template 8 Anti-rotavirus IgA antibody GMC and seropositivity rates – ATP cohort for Immunogenicity

			≥ 20 U/ml				GMC (U/ml)		
			95% CI				95% CI		
Group	Timing	N	n	%	LL	UL	value	LL	UL
HRV LIQ	PRE	244	0	0.0	0.0	1.5	<20	-	-
	PII(M2)	244	206	84.4	79.3	88.7	324.4	253.4	415.3
HRV LYO	PRE	252	0	0.0	0.0	1.5	<20	-	-
	PII(M2)	252	228	90.5	86.2	93.8	331.8	265.0	415.4

HRV LIQ = HRV vaccine liquid formulation Lot C LIQPOOL = Pooled HRV vaccine liquid formulation

HRV LYO = HRV vaccine HRV Lyophilised formulation

[figure not shown]
N = number of subjects with available results

n (%) = number/percentage of subjects with concentration above the cut-off

95% CI = 95% Confidence Interval; L.L =Lower limit; U.L = upper limit

Pre = pre-vaccination

PII (M2) = blood sample taken one month after Dose 2 of HRV vaccine (Visit 3)

Template 9 Reverse cumulative distribution curve for anti-rotavirus IgA antibody concentrations at Visit 3 - ATP cohort for Immunogenicity

CONFIDENTIAL

116194 [DTPA-IPV (INFANRIX-IPV)-061]
 Statistical Analysis Plan Amendment 2 Final

Template 10 Number and percentage of subjects who received study vaccine doses - TVC

		HRV LIQ N = 300		HRV LYO N = 300		Total N = 1200		
VACCINE		Total number of doses received	n	%	n	%	n	%
Pediarix	1	0	0.0	1	0.3	3	0.3	
	2	300	100	299	99.7	1197	99.8	
	3							
Any	Any	300	100	300	100	1200	100	
Hiberix	1	0	0.0	1	0.3	3	0.3	
	2	300	100	299	99.7	1197	99.8	
	3							
Any	Any	300	100	300	100	1200	100	
Prevnar	1	0	0.0	1	0.3	3	0.3	
	2	300	100	299	99.7	1197	99.8	
	3							
Any ON COAD	Any	300	100	300	100	1200	100	

HRV LIQ = HRV vaccine Liquid formulation lot A HRV LIQ = HRV vaccine Liquid formulation lot B

HRV LIQ = HRV vaccine Liquid formulation lot C HRV LYO = HRV vaccine HRV Lyophilised formulation

N = number of subjects in each group or in total included in the considered cohort

n (%) = number/percentage of subjects receiving the specified total number of doses

Any = number and percentage of subjects receiving at least one dose

Template 11 Compliance in returning symptom sheets - TVC

Dose	GROUP	Number of doses	Doses NOT according to protocol	Number of general SS	Compliance % general SS
1	HRV LIQ	298	10	298	100
	HRV LIQ	302	7	302	100
	HRV LIQ	300	6	300	100
	LIQPOOL	900	23	900	100
	HRV LYO	300	6	299	99.7
2	HRV LIQ	297	12	296	99.7
	HRV LIQ	301	6	301	100
	HRV LIQ	300	13	299	99.7
	LIQPOOL	898	31	896	99.8
	HRV LYO	299	9	297	99.3
Total	HRV LIQ	595	22	594	99.8
	HRV LIQ	603	13	603	100
	HRV LIQ	600	19	599	99.8
	LIQPOOL	1798	54	1796	99.9
	HRV LYO	599	15	596	99.5

HRV LIQ = HRV vaccine liquid formulation Lot A

HRV LIQ = HRV vaccine liquid formulation Lot B

HRV LIQ = HRV vaccine liquid formulation Lot C

LIQPOOL = Pooled HRV vaccine liquid formulation

HRV LYO = HRV vaccine HRV Lyophilised formulation

SS = Symptom sheets used for the collection of solicited AEs

Compliance % = (number of doses with symptom sheet return / number of administered doses) X 100

Doses not according to protocol = number of doses with regurgitation or vomiting

Template 12 Incidence and nature of grade 3 symptoms (solicited and unsolicited) reported during the 4-day (Days 0-3) period after vaccination following each dose and overall (Total vaccinated cohort)

		Any symptom			General symptoms			Local symptoms								
		95% CI		95% CI		95% CI		95% CI		95% CI		95% CI		95% CI		
	Group	N	n	%	LL	UL	N	n	%	LL	UL	N	n	%	LL	UL
Dose 2	Combo group	224	18	8.0	4.8	12.4	224	7	3.1	1.3	6.3	224	12	5.4	2.8	9.2
	Control group	227	15	6.6	3.7	10.7	227	6	2.6	1.0	5.7	227	11	4.8	2.4	8.5
Dose 4	Combo group	224	29	12.9	8.8	18.1	224	6	2.7	1.0	5.7	224	26	11.6	7.7	16.5
	Control group	227	29	12.8	8.7	17.8	227	9	4.0	1.8	7.4	227	22	9.7	6.2	14.3
Dose 6	Combo group	224	25	11.2	7.4	16.0	224	8	3.6	1.6	6.9	224	18	8.0	4.8	12.4
	Control group	227	19	8.4	5.1	12.8	227	2	0.9	0.1	3.1	227	18	7.9	4.8	12.2
Overall/dose	Combo group	672	72	10.7	8.5	13.3	672	21	3.1	1.9	4.7	672	56	8.3	6.4	10.7
	Control group	681	63	9.3	7.2	11.7	681	17	2.5	1.5	4.0	681	51	7.5	5.6	9.7
Overall/subject	Combo group	224	60	26.8	21.1	33.1	224	21	9.4	5.9	14.0	224	44	19.6	14.7	25.5
	Control group	227	47	20.7	15.6	26.6	227	14	6.2	3.4	10.1	227	39	17.2	12.5	22.7

Combo group = Subjects received DTPa-IPV/Hib vaccine as a single injection at 2, 4 and 6 months of age

Control group = Subjects received DTPa-IPV and Hib vaccines at different injection sites at 2, 4 and 6 months of age

For each dose and overall/subject:

N = number of subjects with at least one administered dose

n/% = number/percentage of subjects presenting at least one type of symptom whatever the study vaccine administered

For overall/dose:

N = number of administered doses

n/% = number/percentage of doses followed by at least one type of symptom whatever the study vaccine administered

95% CI = exact 95% confidence interval, LL = Lower Limit, UL = Upper Limit

Dose 2, 4 and 6 are the doses where subjects has received study vaccine - DTPa-IPV/Hib vaccine in Combo group and DTPa-IPV and Hib in Control group

CONFIDENTIAL
 116194 [DTPa-IPV (INFANRIX-IPV)-061]
 Statistical Analysis Plan Amendment 2 Final

**Template 13 Incidence of solicited local symptoms reported during the 4-day
(Days 0-3) period after vaccination following each dose and overall
(Total vaccinated cohort)**

Symptom	Type	Combo group					Control group				
					95 % CI					95 % CI	
		N	n	%	LL	UL	N	n	%	LL	UL
Dose 2											
Pain	All	224	108	48.2	41.5	55.0	227	113	49.8	43.1	56.5
	Grade 3	224	5	2.2	0.7	5.1	227	8	3.5	1.5	6.8
Redness (mm)	All	224	133	59.4	52.6	65.9	227	119	52.4	45.7	59.1
	>20	224	4	1.8	0.5	4.5	227	3	1.3	0.3	3.8
Swelling (mm)	All	224	65	29.0	23.2	35.4	227	64	28.2	22.4	34.5
	>20	224	5	2.2	0.7	5.1	227	2	0.9	0.1	3.1
Dose 4											
Pain	All	224	81	36.2	29.9	42.8	227	88	38.8	32.4	45.4
	Grade 3	224	3	1.3	0.3	3.9	227	3	1.3	0.3	3.8
Redness (mm)	All	224	131	58.5	51.7	65.0	227	124	54.6	47.9	61.2
	>20	224	20	8.9	5.5	13.5	227	18	7.9	4.8	12.2
Swelling (mm)	All	224	85	37.9	31.6	44.7	227	78	34.4	28.2	40.9
	>20	224	9	4.0	1.9	7.5	227	4	1.8	0.5	4.5
Dose 6											
Pain	All	224	87	38.8	32.4	45.6	227	78	34.4	28.2	40.9
	Grade 3	224	1	0.4	0.0	2.5	227	3	1.3	0.3	3.8
Redness (mm)	All	224	128	57.1	50.4	63.7	227	122	53.7	47.0	60.4
	>20	224	14	6.3	3.5	10.3	227	14	6.2	3.4	10.1
Swelling (mm)	All	224	96	42.9	36.3	49.6	227	88	38.8	32.4	45.4
	>20	224	6	2.7	1.0	5.7	227	7	3.1	1.2	6.3
Overall/dose											
Pain	All	672	276	41.1	37.3	44.9	681	279	41.0	37.2	44.8
	Grade 3	672	9	1.3	0.6	2.5	681	14	2.1	1.1	3.4
Redness (mm)	All	672	392	58.3	5	62.1	681	365	53.6	49.8	57.4
	>20	672	38	5.7	4.0	7.7	681	35	5.1	3.6	7.1
Swelling (mm)	All	672	246	36.6	33.0	40.4	681	230	33.8	30.2	37.5
	>20	672	20	3.0	1.8	4.6	681	13	1.9	1.0	3.2
Overall/subject											
Pain	All	224	143	63.8	57.2	70.1	227	146	64.3	57.7	70.5
	Grade 3	224	9	4.0	1.9	7.5	227	12	5.3	2.8	9.1
Redness (mm)	All	224	177	79.0	73.1	84.2	227	167	73.6	67.3	79.2
	>20	224	29	12.9	8.8	18.1	227	26	11.5	7.6	16.3
Swelling (mm)	All	224	130	58.0	51.3	64.6	227	121	53.3	46.6	59.9
	>20	224	15	6.7	3.8	10.8	227	11	4.8	2.4	8.5

Combo group = Subjects received DTPa-IPV/Hib vaccine as a single injection at 2, 4 and 6 months of age

Control group = Subjects received DTPa-IPV and Hib vaccines at different injection sites at 2, 4 and 6 months of age

For each dose and overall/subject:

N = number of subjects with at least one documented dose

n% = number/percentage of subjects reporting the symptom at least once

For Overall/dose:

N = number of documented doses

n% = number/percentage of doses followed by at least one type of symptom

95%CI = Exact 95% confidence interval; LL = lower limit, UL = upper limit

Dose 2, 4 and 6 are the doses where subjects has received study vaccine - DTPa-IPV/Hib vaccine in Combo group and DTPa-IPV and Hib in Control group

Grade 3 pain refers to severe significant pain at rest. Prevents normal every day activities.

CONFIDENTIAL
 116194 [DTPA-IPV (INFANRIX-IPV)-061]
 Statistical Analysis Plan Amendment 2 Final

